### **2.3.9 Fatigue Assessment by the Fatigue Pictogram**

Fatigue assessment will be done by the Fatigue Pictogram. The Fatigue Pictogram (FITCH MI *et al.*, 2003) is an illustrated instrument for the assessment of fatigue (ANNEX 2). It has two sets of figures that assess the intensity and impact of fatigue on usual activities and, as it is brief and easy to apply, it is useful for assistance and research. Aiming at comparability between world populations or populations with different diseases, and in view of the recommendations to make cultural adaptations of existing instruments instead of creating new ones, we chose to use it, assigning numbers to each of the images to facilitate quantitative analysis. This scale was validated in Brazil in relation to its psychometric properties in the Brazilian population (MOTA DD *et al.*, 2009)

### **2.3.10 Quality of life assessment**

The assessment of quality of life will be carried out using a generic instrument of 36 items, validated in Brazil and called the SF-36 (Short Form Health Survey). This instrument is a generic quality-of-life assessment questionnaire that is easy to administer and understand. Consisting of 36 items, subdivided into 8 domains, which are: functional capacity, physical aspects, pain, general health status, vitality, social aspects, emotional aspects and mental health. It presents a score that goes from 0 (zero) to 100 (obtained by calculating the *Raw Scale*), where zero corresponds to the worst general health status and 100 corresponds to the best health status. To calculate the domain (aspect to be analyzed), a specific formula is applied, according to the translated and validated SF-36 (Brazier *et al.*, 1992; Lins and Carvalho, 2016)

### **2.3.11 Pilates Method Exercise Protocol (MP)**

Pilates exercise protocol : was developed based on protocols contained in previously published clinical trials whose objective was muscle strengthening or improvement of muscle fatigue. Thus, the protocol developed will perform exercises from the classical repertoire of the Pilates Method, with the use of equipment exclusive

to the Method - such as *Cadillac* , *Ladder Barrel* , *Chair and Reformer* . The sessions will take place twice a week, in groups of up to 3 participants, always in the morning and will last 60 min, with 10 min of warm-up, 40 min of exercises with load and 10 min of relaxation exercises and calm down. All sessions will be performed by a physical therapist specialized in the method, in a specific outpatient clinic. The professional who will conduct the Pilates sessions will execute the proposed protocol and is unaware of the outcomes studied by the project. In figure 3, we present the equipment that will be used in the study.

**Figure 3:** Equipment that will be used. (a) *Combo Chair* , (b) *Cadillac* , (c) *Universal Reformer* , (d) *Ladder barrel*

## 2.4 Outcomes

### 2.4.1 primary outcome

As variables for the primary outcome of this research, it will be the functional performance, resulting from the combination of the PCFS Scale with the Dynamometry of Pressure Para, Test of Strength and of Endurance of the quadriceps muscle.

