#### *maximum voluntary contraction*

[figure not shown]
The assessment of muscle strength and endurance can be obtained by maximal voluntary contraction (MVC). This assessment can be done by instructing the patient to generate as much voluntary force as possible without altering muscle length (symmetrical test) or by encouraging the patient to perform a full range of motion with the greatest possible load (1RM test). In this evaluation, equipment such as tensiometers or dynamometers can be used to quantify the generated isometric force (if there is no change in muscle length). In the case of the 1 RM test, the highest load imposed and that the patient can complete and repeat is considered. As these are volitional techniques, external complicating factors, such as the patient's functional ability and motivation, can generate submaximal contractions and thus underestimate the analysis. However, due to the ease of execution, verbal encouragement and technical experience, little variability has been described in our tests involving maximal voluntary contraction (MVC). In patients with chronic pulmonary dysfunction, the loss of the ability to generate or maintain MVC during knee extension exercise has been representative of muscle fatigue. (SWALLOW EB *et al.*, 2007). Studies have used series of submaximal voluntary contractions in the evaluation of resistance and peripheral muscle fatigue. Usually, relative values of approximately 20-60% of MVC (1RM test or isometrically sustained maximal voluntary contraction ) are required to be sustained until exhaustion, maintaining cadence and rhythm constant or close to it. Resistance is measured by the time the task is maintained. The test should be stopped

when there is a failure to maintain the intensity of the contraction (5% drop) or inability to complete the range of motion or visually there are signs of muscle fatigue, such as fasciculations , for example.

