## **1.4 Goals**

### **1.4.1 Primary / General**

To evaluate the clinical and functional effects of a quarterly Pilates Method exercise program for patients with post-COVID syndrome.

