### **1.4.2 Secondary/Specific**

- Evaluate the effects of pilates exercises on muscle strength and peripheral resistance;

- To compare the effects of Pilates on the levels of fatigue and dyspnea in patients with post-COVID syndrome;

- Correlate the effects of Pilates on peripheral muscle function and symptoms of fatigue and dyspnea in patients with post-COVID syndrome.

- Evaluate the effects of Pilates on the quality of life of patients with post-COVID syndrome

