### **2.3.6.2 Quadriceps Maximum Load Test**

The one-repetition maximum test (1RM) is often used as a measure of muscle strength, whether in the context of physical rehabilitation. In this sense, there is a consensus that the basis for prescribing therapeutic exercises, especially those

performed against resistance TCR) is established through the relationship between the percentage of 1RM and the number of repetitions.

The 1 RM Test will be performed in an extension chair, with adjustments that keep the hip and ankle flexed at 90° and the knee flexed to ensure an angular trajectory of 120° after extension. The 1RM tests will be conducted according to the protocol proposed by Brown and Weir (Brown & Weir, 2001). Before each test, free, light activities involving the tested muscle will be performed, followed by 1 min of stretching for the tested muscle ( in this case, the quadriceps will be tested). After stretching, 3 repetitions were performed with moderate load and after 5min of rest and interval, the 1RM test will be performed, adding weights when necessary, 0.4 to 5kg, totaling up to five attempts. We will record the maximum load as the greatest load lifted in a single movement of full knee extension in an open kinetic chain.

For the reference values, the highest value among the three measures of maximum voluntary contraction in the 1RM test, normalized by the body weight of each individual tested, was used, according to the formula proposed by Magalhães in 2010:  $(\text{Strength (Kg)} / \text{Weight} \times 100)$

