## 2.5 Data analysis

### 2.5.1 Sample size (calculation or justification)

The sample size calculation was done with the “ pwr ” package (CHAMPELY S, 2018) (R package , version 1.2-2, <https://CRAN.R-project.org/package=pwr> ). For the calculation, we considered the mean of 41.3, the standard deviation of 5.05 and a minimal clinically important difference of 4.7 kg between the means of maximum load in the maximal voluntary contraction test (OLIVEIRA IO, 2016) and power based on *Cohen 's model* of 0.8 with a standard deviation of 5.05. Assuming  $\alpha = 0.05$ ,  $\beta = 0.8$ , standard deviation = 5.05 and an effect size proposed by Cohen of 0.93.

This effect size " *d* " is calculated by:

$$d = [(Reference\ average + Minimum\ detected\ change) - reference\ average] / deviation - standard$$

$$d = [( 41.3 + 4.7) - 41.3] / 5.05 \Rightarrow d = 0.93.$$

*pwr* package . in R we have:

```
n = pwr.t.test ( n=NULL, d=0.93, sig.level =0.05, power=0.8, type=" two.sample ", alternative="
two.sided ")
```

$$n = 19.15925$$

$$d = 0.93$$

$$sig.level = 0.05$$

$$power = 0.8$$

$$alternative = two.sided$$

In this way, we use on=established and rounded up to the first integer immediately higher ( $n=20$ ) + 20% to cover any losses. Thus, the minimum number of patients needed in each group will be 24 patients.

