### **2.5.2 control variables**

The control variables will be the peripheral muscle strength established by the handgrip test, by the maximum voluntary contraction test and by the peripheral muscle endurance test. In addition, we will use the mMRC , the quantified fatigue pictogram, the PCFS and the quality of life as control variables.

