### **2.5.5 Statistical analysis plan**

Data analysis will be performed using the SPSS 23.0 program ( Statistical Package for Social Sciences ). Descriptive analysis will be performed for all variables (mean and standard deviation). General Linear Model ( GLMs ) with mixed design will be performed to compare treatment effect size between groups. The pairwise comparison comparisons ) will be performed to verify the mean difference between the Pilates Group and the Control Group in all variables in each period independently.

Intention-to-treat analysis was used using the *Last method. observation Carried Forward* (LOCF) for lost participant data. A significance level of 0.05 and a confidence interval of 95% will be adopted

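### The primary outcome combines four measures with no combining or success rule, and the 80% power was calculated for maximum load alone, so power for the stated primary outcome is undefined

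*Combined protocol and SAP*

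**What the plan says.** Section 2.4.1 defines the primary outcome as "functional performance, resulting from the combination of the PCFS Scale with the Dynamometry of Pressure Para, Test of Strength and of Endurance" of the quadriceps. The components are measured on different scales:

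- PCFS is an ordinal grade from 0 to 4, with death coded separately, and higher is worse (section 2.3.7, Annex 1).
- Handgrip keeps the best value for each hand (section 2.3.6.1).
- Quadriceps strength is a load: "We will record the maximum load as the greatest load lifted in a single movement of full knee extension". The same section, 2.3.6.2, also gives a value normalised by body weight.
- Quadriceps endurance is time to exhaustion (section 2.3.6.3).

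The sample size in section 2.5.1 rests on one variable, with "a minimal clinically important difference of 4.7 kg between the means of maximum load in the maximal voluntary contraction test".

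The analysis in section 2.5.5 is a mixed-design general linear model followed by pairwise comparisons of the "mean difference between the Pilates Group and the Control Group in all variables in each period independently", at a significance level of 0.05.

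The general objective (1.4.1) is "To evaluate the clinical and functional effects of a quarterly Pilates Method exercise program". Strength and endurance appear among the secondary objectives (1.4.2): "Evaluate the effects of pilates exercises on muscle strength and peripheral resistance". The hypotheses in 1.5.1 and 1.5.2 name strength, endurance, fatigue and dyspnea, and do not mention PCFS.

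**The concern.** The primary outcome can be read as one composite score or as four co-primary variables, and the plan completes neither reading. A composite needs a direction, a scaling and weights, because an ordinal grade that improves downward cannot simply be added to a force, a load and a time that improve upward. A co-primary set needs a rule saying whether one success suffices or all four are required. The plan gives none of these, and for handgrip it does not say which hand enters.

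Two things are at stake. First, what counts as a positive trial can be chosen after the data are seen. One pre-specified composite tested once, or an all-four rule, would hold the error at or below 5%, but neither is stated. Counting any one success at 0.05 would not hold it. Second, the 80% power that a reader would attach to the primary outcome belongs to a narrower variable.

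**Working it through.** **The plan's own figure.** Inputs from section 2.5.1: difference 4.7 kg, SD 5.05, two-sided alpha 0.05, power 0.80. The effect size is d = 4.7/5.05 = 0.931, entered as 0.93. A two-sample t-test calculation gives n = 19.159 per arm, as printed. Rounding up gives 20, and 20 × 1.2 = 24. Power for this one variable is 81.8% with 20 analysed per arm, 88.4% with 24 and 94.3% with 30. The figure reproduces, for maximum load only. The document gives no effect size for PCFS, handgrip or endurance.

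**Does another section supply the rule?** Section 2.5.2 lists the components again ("The control variables will be the peripheral muscle strength established by the handgrip test, by the maximum voluntary contraction test", then endurance) beside mMRC, fatigue, PCFS and quality of life, all as control variables and without ranking. Section 2.4.2 separates the secondary outcomes but does not say how the primary ones are judged. Section 2.5.5 names no primary comparison. The objectives and hypotheses do not settle it either.

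**False-positive rate if any one success at 0.05 counts.** For k independent tests it is 1 − 0.95^k.

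- k = 4: 1 − 0.95⁴ = 18.5%.
- k = 5, if both hands are analysed: 1 − 0.95⁵ = 22.6%.
- Four correlated tests, simulated with t-tests at 24 per arm: 17.3%, 15.6%, 13.3% and 9.4% at correlations 0.3, 0.5, 0.7 and 0.9.

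**How far power depends on the missing rule.** This is an illustration with 20 analysed per arm, the number behind the plan's 80%. Assumptions: four roughly normal components (only indicative for PCFS), equal pairwise correlation ρ from 0 to 0.9, and d = 0.93 for strength. The effect size of the other three is assumed to be either 0.93 or 0.5.

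| Rule | All d = 0.93 | Other three d = 0.5 |
|---|---|---|
| All four significant at 0.05 | 45–72% | 3–24% |
| Average z-score composite, one test at 0.05 | about 85% to over 99% | about 49–96% |
| At least one significant at 0.0125 (Bonferroni) | about 75–98% | about 63–78% |

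Two rows can be checked by formula.

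- All four, independent, all d = 0.93: 0.8175⁴ = 0.447.
- Composite: its effect size is the mean d divided by √((1 + 3ρ)/4). With all d = 0.93 this is 0.93/0.5 = 1.86 at ρ = 0 and 0.93/0.962 = 0.967 at ρ = 0.9. With the other three at 0.5, the mean is (0.93 + 3 × 0.5)/4 = 0.6075, giving 1.215 and 0.632.

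Higher correlation raises power under the all-four rule and lowers it under the other two, so the rules cannot stand in for one another. The Bonferroni row is the chance of at least one success. Power for one given component at 0.0125 with d = 0.93 is a different quantity: 63%, 73% and 84% at 20, 24 and 30 per arm.

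**The case against.** The strongest defence is that functional performance is a construct, that strength is its natural anchor, and that sizing a trial on one component is common. That would answer the point if the plan named strength as the anchor or its test as decisive. It does not, and section 1.4.2 places strength among the secondary objectives.

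Three stronger readings are tempting but unsupported:

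- *The trial is underpowered.* A reader might infer this from the all-four row. The documents do not ask for all four, and a composite could have more than 80% power at the same size. The plan also states two totals, 48 (Summary and 2.5.1) and 60 (2.3). Neither total tells a reader what counts as success.
- *The false-positive rate is 18.5%.* That holds only if any one success counts and the tests are independent. The plan states no such rule, and four measures of physical function are likely to be correlated.
- *The planning figures come from a different test.* The literature review (1.1.9.4) allows maximal voluntary contraction to be isometric, saying of the patient: "This assessment can be done by instructing the patient to generate as much voluntary force as possible without altering muscle length". But there the word load goes with the 1RM version, and section 2.3.6.2 speaks of maximum voluntary contraction in the 1RM test, which fits 2.5.1. What remains open depends on the cited source, so it calls for confirmation and is not an established error.

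**Conclusion.** The point stands and must be fixed. The primary outcome has no combining or success rule, no primary test is named, and the stated 80% power applies to maximum load alone. That follows from the text without any assumption. The sample-size arithmetic is sound for the variable it covers.

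The sizes are conditional. The inflated false-positive rate applies only if any one component may count. The power figures rest on assumed correlations and on effect sizes that the documents do not give for three of the four components. Their spread, from 3% to over 99%, shows that power is undefined; no single entry should be used for planning.

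**What to change.** Before outcome data are seen, amend sections 2.4.1 and 2.5.5 in one of two ways, at the sponsor's choice.

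**Option A: match the existing calculation.** Name quadriceps maximum load (2.3.6.2) as the single primary variable. The primary test is the between-group difference at 12 weeks from the mixed-design model, two-sided 0.05. State whether it is analysed in kg or as the body-weight-normalised value; the calculation in 2.5.1 is in kg. Confirm that 41.3, 4.7 and 5.05 refer to that test, and redo the calculation if they do not. PCFS, handgrip (state which hand) and endurance time become secondary. If the figures are confirmed, this adds no patients or assessments. Its price is that the headline claim narrows from function to strength, and PCFS, the only functional-status scale among the four, is no longer primary.

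**Option B: keep functional performance.** Write the composite formula (direction, scaling, weights), or the co-primary success rule with its error control. Replace the stated 80% with the power for that rule under stated effect sizes for each component. This keeps the functional claim but needs a new calculation, and the sample size may change in either direction.

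Under either option, align the objectives (1.4.1, 1.4.2) and hypotheses (1.5.1, 1.5.2) with the choice, and make the ethics submission and registry entry (2.1, 2.2.2) agree.

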## 2.4.2 secondary outcome

Improved quality of life (Questionnaire SF36) and reduced perception of dyspnea during physical activities and ADLs ( mMRC and Borg ).

## 2.5 Data analysis

### 2.5.1 Sample size (calculation or justification)

The sample size calculation was done with the “ pwr ” package (CHAMPELY S, 2018) (R package , version 1.2-2, <https://CRAN.R-project.org/package=pwr> ). For the calculation, we considered the mean of 41.3, the standard deviation of 5.05 and a minimal clinically important difference of 4.7 kg between the means of maximum load in the maximal voluntary contraction test (OLIVEIRA IO, 2016) and power based on *Cohen 's model* of 0.8 with a standard deviation of 5.05. Assuming  $\alpha = 0.05$ ,  $\beta = 0.8$ , standard deviation = 5.05 and an effect size proposed by Cohen of 0.93.

This effect size " *d* " is calculated by:

$$d = [(Reference\ average + Minimum\ detected\ change) - reference\ average] / deviation - standard$$

$$d = [( 41.3 + 4.7) - 41.3] / 5.05 \Rightarrow d = 0.93.$$

*pwr* package . in R we have:

```
n = pwr.t.test ( n=NULL, d=0.93, sig.level =0.05, power=0.8, type=" two.sample ", alternative="
two.sided ")
```

$$n = 19.15925$$

$$d = 0.93$$

$$sig.level = 0.05$$

$$power = 0.8$$

$$alternative = two.sided$$

In this way, we use on=established and rounded up to the first integer immediately higher ( $n=20$ ) + 20% to cover any losses. Thus, the minimum number of patients needed in each group will be 24 patients.

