### **2.3.2 Inclusion criteria**

1. Patients with a previous diagnosis of COVID-19, who required hospitalization and required invasive mechanical ventilation for at least 7 days and who were discharged between August and December 2021 to minimize regression to mean;
2. Both sexes;
3. Older than 18 years.

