### **2.3.6 Peripheral Muscle Assessment**

#### **2.3.6.1 Palm grip dynamometry**

Traditionally, handgrip strength (HGS) tests have been used in rehabilitation to assess the physical condition of the upper limbs, by measuring the strength of the hand and forearm muscles of patients with various disorders in the upper extremity resulting from arthritis, rheumatoid disease , carpal tunnel syndrome, lateral epicondylitis , stroke, traumatic injuries, myopathy , ICU-acquired muscle weakness, critical patient polyneuropathy and neuromuscular diseases (INNES E, 1999; KURILLO GA *et al* ., 2004; MOREIRA D *et al.*, 2004; MOREIRA D *et al.* *al* ., 2003) HGS measurement by

dynamometry presents a good correlation with the functional level of the upper limbs and general health status, being widely used in the selection of therapeutic procedures and monitoring of functional rehabilitation (INNES E, 1999). Manual dynamometry has wide applicability, as it is a low-cost, simple, fast and non-invasive method (GÜNTHER CM *et al.*, 2008) that provides, through HGS values, an indicator of the general health of the evaluated individuals.

The HGS assessment will be performed by a single previously trained investigator, in the morning between 8 am and 12 noon, according to the recommendations of the Brazilian Society of Hand Therapists (SBTM, 2008). The individuals will be positioned seated with the arm adducted parallel to the trunk, shoulder in neutral rotation, elbow flexed at 90°, forearm in fundamental position. Wrist hyperextension of up to 30° and ulnar deviation of up to 15° will be allowed during the tests. Three measurements will be taken from both hands, with a minimum interval of 30 seconds between them. The tests will be performed alternately between the dominant and non-dominant side, to minimize the influence of muscle fatigue. For data analysis, the highest value obtained for each hand will be considered. The dominant hand is defined as the preferred hand for carrying out daily activities. Volunteers will be asked which hand they prefer to carry out activities such as writing, eating and carrying objects. During the execution of the handgrip, the arm will remain immobile, with only permission for the movement of the wrist and finger joints.

Will be used as prediction formulas (NOVAES RD *et al.*, 2009):

- $HGS-D,_{kgf} = 39.996 - (0.382 \times age,_{years}) + (0.174 \times weight,_{kg}) + (13.628 \times sex \text{ (men=1; women=0)})$

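### The planning SD of 5.05 kg is not shown to apply to the enrolled population, so the stated 80% power is unverified, and the strength comparison makes no use of sex or an explicit baseline adjustment

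*Combined protocol and SAP*

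**What the plan says.** Section 2.5.1 bases the sample size on one variable: "we considered the mean of 41.3, the standard deviation of 5.05 and a minimal clinically important difference of 4.7 kg". It cites a single 2016 source and gives no sex mix, age range, health status or test method for the people that source studied. The source does not appear in the References. The calculation is a two-sided, two-sample t-test with "sig.level =0.05, power=0.8". It gives 20 per arm, raised to 24 for losses. The Summary accordingly states 48 patients, while section 2.3 states 60, or 30 per arm.

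Section 2.3.2 admits both sexes and anyone "Older than 18 years", with no upper age limit, after hospitalisation for COVID-19 with at least 7 days of invasive ventilation. Section 2.2 describes electronic randomisation and mentions no stratification.

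Section 2.3.6.1 gives equations for expected handgrip strength, introduced by "Will be used as prediction formulas". They contain terms for sex, age and body weight.

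Section 2.5.5 plans a mixed-design general linear model, together with pairwise group comparisons carried out separately at each time point. It names no covariates.

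**The concern.** A source from 2016 cannot have sampled COVID-19 survivors, and nothing in the protocol argues that its SD carries over to them. An SD of 5.05 kg on a mean of 41.3 kg is a coefficient of variation of 5.05 / 41.3 = 12.2%. That is narrow for a strength measure in kilograms taken across both sexes and all adult ages. The protocol's own handgrip equations show strength varying materially with sex, age and weight.

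If the SD among enrolled patients is larger, the effect size of 0.93 is too optimistic for the t-test that was sized. A null result would then be read against an 80% power that the trial did not have. Maximum load is the only variable used for sizing, and quadriceps strength is a component of the primary outcome in section 2.4.1. The pairwise comparisons at each time point carry the full between-person spread, and they are also exposed to any chance imbalance between the arms in sex.

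**Working it through.** **1. The plan's own figure.** Inputs from 2.5.1: difference 4.7 kg, SD 5.05 kg, two-sided alpha 0.05, power 0.80.

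- d = 4.7 / 5.05 = 0.93.
- The noncentral-t calculation gives n = 19.16, rounded up to 20. Then 20 x 1.2 = 24.

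The stated n reproduces, so the arithmetic is not at fault. The question is the SD that goes into it.

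**2. How much margin there is.** The largest SD that keeps 80% power for 4.7 kg in an unadjusted two-sample t-test is:

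| Evaluable per arm | Largest SD |
|---|---|
| 20 | 5.17 kg |
| 24 | 5.69 kg |
| 30 | 6.39 kg |

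At 20 per arm the margin over 5.05 kg is 0.12 kg.

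**3. Illustrative SDs.** The documents give no SD for quadriceps load in this population. The only figures on how strength spreads are the handgrip equations in 2.3.6.1:

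- dominant hand: sex 13.628 kg, age 0.382 kg per year, weight 0.174 kg per kg;
- non-dominant hand: sex 9.274, age 0.420, weight 0.110.

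Assumptions, none of them from the documents: age SD 12 years, weight SD 15 kg, and sex, age and weight independent. With a proportion p of men, the SD explained by the equation is

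sqrt[ sex² x p(1 − p) + (age x 12)² + (weight x 15)² ].

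- Dominant, p = 0.5: sqrt(6.81² + 4.58² + 2.61²) = 8.6 kg
- Non-dominant, p = 0.5: sqrt(4.64² + 5.04² + 1.65²) = 7.0 kg
- Dominant, p = 0.9: sqrt(4.09² + 4.58² + 2.61²) = 6.7 kg
- Non-dominant, p = 0.9: sqrt(2.78² + 5.04² + 1.65²) = 6.0 kg

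These exclude residual variation between people. They describe handgrip, so they show a plausible size and are not an estimate for quadriceps load.

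**4. Unadjusted power for 4.7 kg.**

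| SD (kg) | 20 per arm | 24 per arm | 30 per arm |
|---|---|---|---|
| 5.05 | 82% | 88% | 94% |
| 6.0 | 68% | 76% | 85% |
| 6.7 | 58% | 66% | 76% |
| 7.0 | 54% | 62% | 72% |
| 8.6 | 39% | 46% | 55% |
| 10 | 30% | 36% | 43% |

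**5. What baseline adjustment could recover.** With a pre-post correlation r, adjusting for baseline reduces the SD to SD x sqrt(1 − r²). The documents give no r, so the values below are assumed, with an SD of 8.6 kg:

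- r = 0.8: effective SD 8.62 x 0.60 = 5.17 kg; power 80% / 87% / 93% at 20 / 24 / 30 per arm.
- r = 0.7: effective SD 8.62 x 0.714 = 6.16 kg; power 65% / 74% / 83%.

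To bring the effective SD back to 5.05 kg, r must be sqrt(1 − (5.05 / SD)²): about 0.69 at an SD of 7 kg, 0.78 at 8 kg and 0.86 at 10 kg.

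**The case against.** The strongest reply is that the calculation in 2.5.1 is not the planned analysis. Everyone is measured before and after, and the mixed-design model in 2.5.5 has a group-by-time term that works on within-person change. Stable differences due to sex, age and body size largely cancel there. This stands: at an SD of 8.6 kg and a correlation of 0.8, the change-score comparison has 76% / 83% / 91% power at 20 / 24 / 30 per arm. It does not rescue the stated 80%, because the plan gives no correlation and does not say that the group-by-time term carries the inference. The separate comparisons at each time point still use the unadjusted SD.

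Other points also stand. The recruiting hospital may supply a homogeneous, mostly male sample. The grip floors in 2.3.3 trim the weakest patients. With 30 per arm (2.3) the tolerance is wider than with 24. Section 2.3.6.2 expresses 1RM relative to body weight, at least for reference values, so the analysed scale may not be kilograms at all; in that case a power figure in kilograms does not size it.

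A reader might infer that an SD of 5.05 kg is impossible here: in a 50:50 mix a sex gap of G contributes G / 2, so any gap above 2 x 5.05 = 10.1 kg would rule it out. The documents do not support that. They give no sex gap for quadriceps load. The dominant-hand term (13.628 kg) exceeds 10.1, but the non-dominant term (9.274 kg) does not, and a 50:50 mix is itself an assumption.

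**Conclusion.** The point holds as one of missing support. The SD of 5.05 kg comes from an undescribed source that predates COVID-19 and is not shown to apply to the patients in 2.3.2. The 80% power is conditional on that SD, with little tolerance: 5.17 kg at 20 evaluable per arm and 5.69 kg at 24.

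Two stronger readings should be resisted. One is that the source cannot describe a mixed-sex, all-adult sample. Its date rules out COVID-19 survivors, but its sex and age mix is unknown and may have been broad. The other is that true power is around 40% to 55%. Those figures need an SD of 8.6 kg, obtained from handgrip, the dominant-hand equation, an even sex mix and assumed spreads of age and weight, all analysed without baseline. With 90% men the same method gives 6.0 to 6.7 kg, and a correlation near 0.8 would restore about 80% even at 8.6 kg with 20 per arm.

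What remains is a power claim that cannot be verified, and a per-time-point comparison that leaves removable between-person spread in the error term.

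**What to change.** - **Section 2.5.5:** compare post-treatment strength between groups in a model with sex and the baseline value of the same measure as covariates, in place of unadjusted comparisons at each time point. Both covariates are readily available at entry.
- **Section 2.5.1:** describe the population behind the 41.3 / 5.05 / 4.7 kg figures. Present 80% as conditional on an SD of 5.05 kg, and show power over a range of SDs (for example 5 to 10 kg) with the assumed pre-post correlation stated. Use one sample size throughout, since 48 and 60 give different tolerances, and say whether the analysed scale is kilograms or percent of body weight.
- **Section 2.2 (optional):** stratify the electronic allocation by sex. Stratification limits imbalance; it is the model term that removes the spread.

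Cost: rewording of two sections and one or two degrees of freedom in the model. The stated power may look less favourable. No extra patients or measurements are needed.
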